## **Safety End Points**

1. Need for initiation of second vasoactive medication and/or MAP < 60
2. Development of acute kidney injury, based on eGFR value < 30ml/min/1.73m^2
3. Adverse events reflecting urinary tract infection, genital infection, bone fracture, and diabetic ketoacidosis

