The patient's treating physician will be able to override randomization assignment if the physician determines that the assignment is not in the patient's best interest. These patients would be kept on study and their data would be used for observational research within this study.

Data points to be collected: Leveled invasive hemodynamics measured via pulmonary artery catheter at end expiration, standing weights, intake and outputs, blood glucose from basic metabolic panels (BMP) taken at those time points, HbA1C (if not within 3 months), blood pressure (cuff pressure), vasoactive doses, and renal function (measured by serum creatinine and estimated GFR) will be captured at multiple time points during CCU admission, as described below. All data points collected for use in this study are being measured as part of the patient's routine care.

**(1) Cardiac catheterization lab prior to CCU arrival:** Initial baseline hemodynamics obtained in the cardiac catheterization lab prior to CCU arrival will be collected.

- a) Cardiac index (L/min/m^2) by Indirect Fick Method
- b) Right atrial pressure (RAP) (mmHg)
- c) Pulmonary artery systolic pressure (PASP) (mmHg)
- d) Mean pulmonary artery pressure (mPA) (mmHg)
- e) Pulmonary artery diastolic pressure (PADP) (mmHg)
- f) Pulmonary capillary wedge pressure (PCWP) (mmHg)
- g) Pulmonary artery pulsatility index (PAPI)
- h) Right ventricular stroke work index (RVSWI) (mmHg L m^-2)
- i) Systemic vascular resistance (SVR) (dynes/sec/cm^5)
- j) Pulmonary vascular resistance (PVR) (dynes/sec/cm^5)
- k) Systolic, diastolic, and mean blood pressure (SBP/DBP/MAP) (mmHg)
- l) Aortic pulsatility index (API)

**(2) Hour 0 – Leveled hemodynamics,** repeated within two hours of arrival to CCU bed from cardiac catheterization lab prior to SGLT2i administration/equivalent if randomized to no SGLT2i arm, will be collected. All baseline data points to be collected at this time.

- a. Cardiac index (L/min/m^2)
- b. RAP (mmHg)
- c. PASP (mmHg)

- d. mPA (mmHg)
- e. PADP (mmHg)
- f. PCWP (mmHg)
- g. PAPi
- h. RSVWI (mmHg L m^-2)
- i. SVR (dynes/sec/cm^5)
- j. PVR (dynes/sec/cm^5)
- k. SBP/DBP/MAP
- l. API
- m. Standing weight
- n. Urine output
- o. Blood glucose taken from BMP
- p. HbA1c
- q. Current Vasoactive doses
- r. Renal function (serum Creatinine, serum eGFR)
- s. Total diuretic dose

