The patient's participation in the study will end after completion of 4 doses of the SGLT2i or sooner if patient is transferred out of the CCU and continuous hemodynamic monitoring is discontinued, or if patient develops any of the safety end points as listed below. The physician will discuss the ongoing treatment plan with the patient at this point.

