## **Inclusion Criteria**

1. Age  $\geq$  18 years old
2. Reduced ejection fraction (HFrEF) of 40 or less
3. Estimated glomerular filtration rate (eGFR)  $> 30\text{ml/min}/1.73\text{m}^2$
4. Admitted to CCU by advanced heart failure service for decompensated heart failure requiring continuous hemodynamic monitoring with a pulmonary artery catheter

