## **Exclusion Criteria**

1. Diagnosis of type 1 DM
2. eGFR  $< 30\text{ml/min}/1.73\text{m}^2$
3. age  $< 18$  years old
4. Jehovah's witnesses
5. Diagnosis of group 1 pulmonary arterial hypertension
6. Insulin requirement above standard low dose sliding scale
7. Patients with a history of DKA
8. Allergies to SGLT2i medications
9. History of intolerance to SGLT2i medications
10. Patients listed for cardiac transplantation or on mechanical support
11. Pregnant or breastfeeding

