### **Potential Risks**

SGLT2i have been shown to have beneficial effects on renal function (5,20). However, due to its direct effect on the kidneys, SGLT2i are labeled for patients with eGFR  $\geq 20\text{ml/min}/1.73\text{m}^2$  or GFR  $\geq 30\text{ml/min}/1.73\text{m}^2$  depending on the medication. Due to this, we will exclude patients with eGFR  $< 30\text{ml/min}/1.73\text{m}^2$ . Increased risk of genital mycotic infections (i.e. vaginitis and balanitis), urinary tract infections, pyelonephritis, urosepsis, and perineal necrotizing fasciitis have been reported, but only genital infections have been shown to be a significant risk in large randomized trials (3-5). Additionally, there has been a small increased risk of diabetic ketoacidosis associated with the use of SGLT2i, though this was predominantly in patients on insulin, who will not be included in this study (5). Lastly, canagliflozin was associated with an elevated risk of lower limb amputation and bone fractures compared to placebo in the CANVAS trial, but this was not seen with the CREEDANCE trial of canagliflozin, or in other SGLT2i randomized controlled trials, including the EMPA-REG OUTCOME, DECLARE-TIMI-58, DAPA-HF, EMPEROR-Reduced trials completed for empagliflozin and dapagliflozin (4). We will not be using canagliflozin in this study.

The adverse reactions of dapagliflozin in order of incidence include female genital mycotic infections, nasopharyngitis, urinary tract infection, back pain, increased urination, male genital mycotic infections, nausea, influenza, dyslipidemia, constipation, dysuria, pain in extremity, increase in creatinine, increase in hematocrit, dyslipidemia, hypersensitivity reactions, urosepsis, necrotizing fasciitis of the perineum.

Since patients are randomized to two routine care arms, we do not believe there is additional risk incurred by participating in this study. The treating physician will be notified of the randomization assignment and can override the assignment if they believe it to be in the best interest of the patient. While SGLT2 inhibitor therapy is approved for use in patients with HFrEF, there is not sufficient data guiding its use in the ICU-setting in patients with acute decompensated heart failure. If benefit is shown in the SGLT2i population, the arm without SGLT2i would lose the hypothesized benefit of renal and cardiovascular benefits during the CCU stay.

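### The kidney safety event is a crossing of eGFR 30, not a change from Hour 0, so its count should not be read as acute kidney injury

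*Combined protocol and SAP*

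**What the plan says.** All places are in the combined protocol and SAP.

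- **Safety End Points, item 2:** "Development of acute kidney injury, based on eGFR value" below 30 ml/min/1.73 m². This is the only kidney item of the three. It mentions no Hour 0 value, no size of change and no confirmatory reading.
- **Inclusion Criteria, item 3:** "Estimated glomerular filtration rate (eGFR") must be above 30. **Exclusion Criteria, item 2** removes patients below 30.
- **Potential Risks:** the limit is explained by labelling: "However, due to its direct effect on the kidneys, SGLT2i are labeled for patients with eGFR" at or above 20 or 30, depending on the product. It continues: "Due to this, we will exclude patients with eGFR" below 30. The explanation concerns eligibility and does not mention the safety end point.
- **Study Design, Study Procedures, and Statistical Procedures:** "renal function (measured by serum creatinine and estimated GFR) will be captured at multiple time points during CCU admission". The item "Renal function (serum Creatinine, serum eGFR") is on the list at Hour 0, before the first dose or its equivalent, and again at Hours 3 and 27. It is also listed at Hours 51 and 75, which apply only while vasoactives and the catheter are still in use.
- **Outcomes:** the secondary list opens with changes and includes renal function, without a metric, a time point or a link to the safety event.
- **End of participation** (last paragraph before Outcomes): participation stops after the fourth dose or earlier, "or if patient develops any of the safety end points as listed below".

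**The concern.** The label names an acute change within a patient, but the criterion is a level that is the same for everyone. A patient who starts just above 30 meets it after a trivial fall. A patient who starts high can lose most of their eGFR without meeting it. The item therefore sorts patients largely by where they began.

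What is at stake is how the safety result is read. Potential Risks refers to a direct effect of the drug class on the kidneys and lists a rise in creatinine among the adverse reactions, so readers will look at this line of the safety report. If the count appears there as acute kidney injury, it may be taken for a rate of acute injury, which the stated rule does not measure.

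**Working it through.** The protocol gives no event rate, sample size or power for kidney injury, so there is no stated figure to reproduce. The check applies the stated rule to a range of starting values.

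**Inputs.** The threshold of 30 ml/min/1.73 m² comes from Safety End Points. Starting values e above 30 are allowed by Inclusion Criteria; the particular values below are illustrations, because no eGFR distribution is given. The starting value is taken to be the Hour 0 reading and to be above 30. The protocol does not say which reading decides eligibility.

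**Step 1: the fall that must be exceeded to count.** Formula: (e − 30)/e.

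| Hour 0 eGFR | Calculation | Fall to be exceeded |
|---|---|---|
| 31 | 1/31 | 3.2% |
| 35 | 5/35 | 14.3% |
| 40 | 10/40 | 25.0% |
| 60 | 30/60 | 50.0% |
| 90 | 60/90 | 66.7% |

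**Step 2: two patients under the same rule.**
- From 31 to 29.9: (31 − 29.9)/31 = 3.5%. Counted.
- From 90 to 31: (90 − 31)/90 = 65.6%. Not counted.

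**Step 3: the same relation read the other way.** A fall of fraction f is counted only if the starting value is below 30/(1 − f).
- f = 0.10: 30/0.90 = 33.3
- f = 0.25: 30/0.75 = 40.0
- f = 0.50: 30/0.50 = 60.0

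These fractions show the dependence on the starting value. They are not proposed definitions.

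**Step 4: what early exit does to a change-based event.** Reaching eGFR below 30 ends participation. A patient who leaves at Hour 3 for this reason has one of the two fixed post-dose readings (Hours 3 and 27). Suppose, for illustration only, that the sponsor chose a 25% fall in eGFR. By Step 3, a patient who starts below 40 can cross 30, and leave, before reaching that fall. A patient who starts at 40 or above and crosses 30 has already fallen by more than 25%. The loss of information therefore falls mainly on patients who start near 30.

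**The case against.** Several counter-arguments are sound and limit the point.

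- **Large falls above 30 are not lost.** A reader might infer that a fall from 90 to 31 goes unreported. The documents do not support that. Read naturally, Outcomes makes change in renal function a secondary outcome, and creatinine and eGFR are recorded from Hour 0 onward, so such a fall would enter a named outcome. What remains is that this outcome has no metric and no link to the safety event, so it does not supply an event definition.
- **The shared number is not itself a fault.** A reader might object to the event threshold being equal to the entry floor. Because entry requires a value above 30, a later value below 30 is a genuine new crossing, and the wording of the safety item implies a new event. What the rule leaves uncontrolled is the size of the fall.
- **A fixed floor is coherent as a reason to end participation.** A reader might infer that the participation rule and the safety list conflict. They do not: the first refers to the list and the second supplies it.
- **No bias between arms is shown.** The dependence on starting eGFR applies to both randomised arms. With 20 patients per arm, the number who start near 30 may differ by chance, but that is not a systematic effect.
- **The consequence is modest.** The protocol sets out no between-arm comparison of safety events, calls itself an initial pilot, follows 40 patients for less than 4 days, and prints the threshold beside the label. Potential Risks also reports beneficial renal effects of the class. This lowers the severity, but it does not make a crossing of 30 a measure of acute change.

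**Conclusion.** The point holds as a minor one. Following the rule as written gives a count of patients who newly crossed an eGFR of 30, and that count should not be presented as acute kidney injury. Across the illustrative starting values from 31 to 90, the fall needed ranges from just over 3.2% to just over 66.7%.

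The arithmetic rests only on the threshold of 30 and the chosen starting values. How many patients would be classified differently under a change-based definition cannot be determined, because the documents give no baseline eGFR distribution. The conclusion concerns the name and meaning of one safety item. It does not extend to the primary outcomes, to bias between arms or to the clinical rule for ending participation.

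**What to change.** For the safety analysis only:

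1. Report the existing item under the name eGFR below 30, not as acute kidney injury.
2. Add a per-patient kidney event defined as a pre-specified change from Hour 0 in serum creatinine or eGFR. Tie it to the renal-function secondary outcome so that both use the same metric. The sponsor sets the measure and the size of the change.
3. Leave the rule on ending participation unchanged and with the sponsor. State in the report that patients who leave at eGFR below 30 have no later study values, and give the number who left before meeting the event in item 2.

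**Cost.** No new measurements are needed: creatinine and eGFR are already on the list at Hour 0 and at every later measurement time. The work is rewording one safety item and adding one analysis definition. The downside is that one more definition has to be reported, and it is only partly observed in patients who leave early, mainly those who start near 30.

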## **Outcomes**

Primary outcome: Change in Indirect Fick cardiac index and change in PCWP

Secondary outcomes: changes in pulmonary artery pulsatility index (PAPi), Right atrial pressure (RAP), pulmonary artery systolic pressure (PASP), mean pulmonary artery pressure (mPA), pulmonary artery diastolic pressure (PADP), right ventricular stroke work index (RWSWI), systemic vascular resistance (SVR), pulmonary vascular resistance (PVR), mean arterial pressure (MAP), renal function, 24 hour urine output, changes in weight, changes in vasoactive dose, and blood glucose levels

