## **Data and Safety Monitoring**

Data safety measures will be maintained as above. Appropriate CBIS and risk management personnel will be contacted immediately if any data loss is suspected. All patients in this study are closely monitored throughout the duration of activity in this study as, by nature, they are in the CCU. Any study-related adverse events will be reported to the IRB according to the IRB's reporting requirements. Adverse events related to the SGLT2i will be reported to the manufacturer or directly to the FDA as would normally occur for safety reporting of routine medications.

40 subjects in this initial pilot study are followed for less than 4 days. We believe that this is the minimum required to clarify potential benefit of SGLT2 inhibitor therapy in the acute setting in patients with acute decompensated heart failure. We do not anticipate adequate data prior to study completion evidencing benefit that would justify study stoppage or redesign.

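### All-cause death is not recorded anywhere in the plan, and there is no rule for how a patient who dies or exits early enters the change in CI and PCWP

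*Combined protocol and SAP*

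**What the plan says.** The Safety End Points section has three items: "Need for initiation of second vasoactive medication and/or MAP < 60"; "Development of acute kidney injury, based on eGFR value" below 30; and "Adverse events reflecting urinary tract infection, genital infection, bone fracture, and diabetic ketoacidosis".

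The Outcomes section gives "Primary outcome: Change in Indirect Fick cardiac index and change in PCWP", followed by secondary haemodynamic, renal, urine-output, weight, vasoactive-dose and glucose measures. It names no time point, analysis method or rule for missing values.

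The end-of-participation paragraph, after the hourly schedule, stops participation after four doses. It stops earlier when the patient leaves the unit and catheter monitoring has ceased. A last clause adds the safety exit: "or if patient develops any of the safety end points as listed below".

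Data and Safety Monitoring says "Any study-related adverse events will be reported to the IRB according to the IRB's reporting requirements". It adds that events related to the drug class go to the manufacturer or the FDA.

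Death and mortality are mentioned only in the rationale, the Potential Benefits section and the references, and always about other studies.

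**The concern.** The participants have acute decompensated heart failure, are in intensive care and, according to Study Subjects, need vasoactive support. Death is the most serious event that can happen to them. The safety list names genital infection and bone fracture but not death.

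Two things are at stake. The first is the safety comparison: a difference in deaths between arms could go unrecorded, or be seen only as a MAP reading below 60. The second is the primary comparison. Both primary outcomes need a later catheter reading, and patients who die or leave early may not have one. If they are left out and the losses are unequal between arms, the arm that loses its sickest patients looks better on CI and PCWP.

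**Working it through.** **Step 1. Where a death could be recorded.**

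| Place in the protocol | Would a death be captured? |
|---|---|
| Items collected at each time point | No: haemodynamics, weight, urine output, glucose, HbA1c, vasoactive and diuretic doses, renal function |
| Outcomes | No |
| Safety End Points | No; at most indirectly through MAP < 60 |
| End of participation | Not mentioned |
| Data and Safety Monitoring | Only if judged study-related |

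**Step 2. Follow one deteriorating patient.** MAP falls below 60, or a second vasoactive is started. That is a safety end point, so participation ends. The patient dies some hours later. Nothing in the plan asks for data after participation ends. Potential Risks states that participation is not believed to add risk, because both arms are routine care, so the death could readily be classed as unrelated to the study. The record would then look the same as that of a patient with one brief low pressure who recovered.

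**Step 3. What happens to the change score.** Readings are taken at Hours 0, 3 and 27, and at Hours 51 and 75 only if vasoactives and the catheter are still in use. A patient lost before Hour 3 has no change score. One lost between Hours 3 and 27 has a change to Hour 3 but not to Hour 27. One lost after Hour 27 has both. Which losses matter depends on a primary reading that is not named.

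**Step 4. The plan's own figures.** The sample-size statement gives 16 per arm for 5 mmHg and 18 per arm for 0.75 L/min/m², at 80% power and alpha 0.05. It gives no SD, so these numbers cannot be reproduced independently. Assuming a two-sided test, n = 2(1.960 + 0.842)² SD²/δ², so SD = δ / (2.802 × √(2/n)).

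- PCWP: 5 / (2.802 × √(2/16)) = 5.05 mmHg (4.88 with the t distribution).
- CI: 0.75 / (2.802 × √(2/18)) = 0.80 L/min/m² (0.78 with the t distribution).

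**Step 5. Worst-case shift.** Assume no treatment effect, 20 normally distributed changes per arm, all losses in one arm, and exactly the k worst values lost. The three most extreme of 20 standard normal values have expected distances from the mean of 1.867, 1.408 and 1.131. The mean of those who remain moves in the favourable direction by the sum of the first k, divided by 20 − k.

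| k lost | Shift (SD) | PCWP (× 5.05) | CI (× 0.80) | Share of target effect |
|---|---|---|---|---|
| 1 | 1.867/19 = 0.098 | 0.5 mmHg | 0.08 | about 10% |
| 2 | 3.275/18 = 0.182 | 0.9 mmHg | 0.15 | 18–19% |
| 3 | 4.406/17 = 0.259 | 1.3 mmHg | 0.21 | 26–28% |

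**Step 6. How likely is any death?** The documents give no mortality figure. For assumed risks over follow-up of 1%, 2%, 5% and 10%, the chance of at least one death among 40, 1 − (1 − p)⁴⁰, is 33%, 55%, 87% and 99%.

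**The case against.** A reader might infer that every patient who dies drops out of both change scores and that the primary comparison is made in survivors only. The documents do not support that. They state no time point and no missing-value rule, and Step 3 shows that a death after Hour 3 or Hour 27 can leave a usable change score. If the primary reading were Hour 3, two hours after the first dose, the exposed window would be very short. Omission is a foreseeable default, not a stated rule.

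A reader might also infer that an ICU death would go unreported to the IRB. That depends on the IRB's own requirements, which are not in the documents. What can be said is that the protocol's wording is limited to study-related events, and that a report to an IRB is not a count by arm.

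The figures in Step 5 are deliberately extreme. Three losses against none means 15% in one arm and 0% in the other before the reading, within a follow-up of less than four days. Similar losses in both arms would largely cancel. If prognosis and haemodynamic change correlate at 0.5, the shifts halve to about 0.05 to 0.13 SD. The standard error of the difference at 20 per arm is √(2/20) = 0.32 SD, so the one-loss shift is under a third of it.

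Finally, death is only one route out. Safety exits, transfer and catheter removal also truncate the readings and may be commoner, so a rule for deaths alone would leave most of the problem open. All of this stands as a limit on the primary-outcome part. None of it answers the absence of death from the safety data.

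**Conclusion.** The point holds in two parts of unequal strength.

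The firm part is textual and needs no assumption: all-cause death is not a collected item, an outcome or a safety end point. Because participation stops at a safety end point, a death soon afterwards need not be recorded. As written, the safety comparison can miss it.

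The second part is conditional. The plan does not say how a patient who dies or exits early enters the change in CI and PCWP. If such patients are omitted, the comparison applies only to those who survive and stay monitored. The bias is at most about 0.10 to 0.26 SD for 1 to 3 losses. That bound rests on one-sided loss of exactly the worst values, normally distributed changes, back-solved SDs and an unknown mortality. The likely effect over less than four days is smaller.

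**What to change.** 1. In Safety End Points, add all-cause death as a separate item, counted by randomised arm whatever the attributed cause.
2. In the end-of-participation paragraph, state that vital status is still taken from the chart to Hour 75 for every randomised patient, including those who left for a safety end point or were transferred. Without this sentence, item 1 would miss the deaths described in Step 2.
3. Optional: once Outcomes names the primary reading, add one sensitivity analysis per primary outcome. Patients who die before that reading receive the worst rank and the arms are compared by a rank test, reported beside the mean difference. The same rule should say how other early exits are treated.

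Items 1 and 2 cost two sentences and a chart check, and change no treatment or clinical rule. Item 3 costs one extra analysis per outcome and depends on the primary reading being fixed. It gives no estimate in mmHg or L/min/m², and with no deaths or one it will differ little from an ordinary rank test. It should therefore supplement the main analysis, not replace it.

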#### (4) **Hour 3**

- a. Cardiac index (L/min/m^2)
- b. RAP (mmHg)
- c. PASP (mmHg)
- d. mPA (mmHg)
- e. PADP (mmHg)
- f. PCWP (mmHg)
- g. PAPi
- h. RSVWI (mmHg L m^-2)
- i. SVR (dynes/sec/cm^5)
- j. PVR (dynes/sec/cm^5)
- k. SBP/DBP/MAP
- l. API
- m. Standing weight
- n. Urine output
- o. Blood glucose taken from BMP
- p. HbA1c
- q. Current Vasoactive doses
- r. Renal function (serum Creatinine, serum eGFR)
- s. Total diuretic dose

(5) **Hour 27** - 2 hours after 2nd dose of SGLT2i, which will be administered 24 hours after first dose, or equivalent time period after which the dose would have been given for the No-SGLT2i arm.

- a. Cardiac index (L/min/m^2)
- b. RAP (mmHg)
- c. PASP (mmHg)
- d. mPA (mmHg)
- e. PADP (mmHg)
- f. PCWP (mmHg)
- g. PAPi
- h. RVSWI (mmHg L m^-2)
- i. SVR (dynes/sec/cm^5)
- j. PVR (dynes/sec/cm^5)
- k. SBP/DBP/MAP
- l. API
- m. Standing weight
- n. Urine output
- o. Blood glucose taken from BMP
- p. HbA1c
- q. Current Vasoactive doses
- r. Renal function (serum Creatinine, serum eGFR)
- s. Total diuretic dose

**(6) Hour 51 & Hour 75 - if vasoactives are still required and pulmonary artery catheter is still being used for routine clinical care**, we will continue SGLT2i for up to 4 doses, and the additional invasive hemodynamics repeated two hours after each dose will be collected.

- a. Cardiac index (L/min/m^2)
- b. RAP (mmHg)
- c. PASP (mmHg)
- d. mPA (mmHg)
- e. PADP (mmHg)
- f. PCWP (mmHg)
- g. PAPi
- h. RVSWI (mmHg L m^-2)
- i. SVR (dynes/sec/cm^5)
- j. PVR (dynes/sec/cm^5)
- k. SBP/DBP/MAP
- l. API
- m. Standing weight
- n. Urine output
- o. Blood glucose taken from BMP
- p. HbA1c
- q. Current Vasoactive doses
- r. Renal function (serum Creatinine, serum eGFR)
- s. Total diuretic dose

Leveled invasive hemodynamic measurements, standing weights, intake and outputs, blood glucose, blood pressure, vasoactive doses, and renal function will stop being collected for the

study after the fourth dose of SGLT2i, or equivalent timing for those randomized to the No-SGLT2i arm.

The leveled hemodynamic measurements measured via a pulmonary artery catheter at end expiration will be collected. A picture will be taken and shown to an Advanced HF attending not involved with the patient's current care and blinded to treatment for interpretation.

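### Time observed for infection, fracture and ketoacidosis depends on the patient's course, so raw counts by arm are not comparable, and no acidosis marker is abstracted

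*Combined protocol and SAP*

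**What the plan says.** The Safety End Points section has three items. The first two are haemodynamic (a second vasoactive drug or MAP below 60) and renal (eGFR below 30). The third is "Adverse events reflecting urinary tract infection, genital infection, bone fracture, and diabetic ketoacidosis", with no definition, method of ascertainment or observation period.

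The end of observation is set in the Study Design section. The paragraph just before Outcomes says that participation "will end after completion of 4 doses of the SGLT2i or sooner if patient is transferred out of the CCU" with monitoring discontinued, "or if patient develops any of the safety end points as listed below". The first dose is at Hour 1; for the second, the schedule says "which will be administered 24 hours after first dose". The last two collections are conditional: "Hour 51 & Hour 75 - if vasoactives are still required and pulmonary artery catheter is still being used for routine clinical care". Data and Safety Monitoring sums this up: "40 subjects in this initial pilot study are followed for less than 4 days". No later contact or record review is described.

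On laboratory data, the list of data points takes "blood glucose from basic metabolic panels (BMP) taken at those time points", together with serum creatinine and eGFR. Bicarbonate, anion gap, ketones and pH do not appear there or in the lists for each time point.

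**The concern.** Observation of the item 3 events is not cut off at a common time. It ends when the patient improves enough to leave the CCU, or deteriorates enough to reach a haemodynamic or renal end point. Both routes could plausibly be affected by treatment. The rationale section hypothesises that SGLT2i improves haemodynamics, which could bring earlier CCU exit in the treated arm. Potential Risks lists a rise in creatinine among the reactions to dapagliflozin but also describes renal benefit, so the eGFR stop could act in either direction. If the arms are watched for different lengths of time, a difference in raw counts, or the lack of one, may reflect time observed rather than risk.

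Ketoacidosis is named as an end point, but the study data set holds no measure of acidosis against which a reported case could be confirmed or a missed one recognised.

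What is at stake is the reading of the safety table. The haemodynamic and renal items can be measured within the window and are not in question.

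**Working it through.** **1. Longest window, and the plan's own figure.** Inputs from the schedule: first dose at Hour 1, 24 hours between doses, up to 4 doses, measurement 2 hours after each dose.
- Dose 4: 1 + 3 × 24 = Hour 73. Last measurement: 73 + 2 = Hour 75.
- 75 / 24 = 3.1 days, which agrees with the plan's statement of under 4 days.

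**2. How much the window can vary.** If vasoactives or the catheter are no longer in use after the second dose, the last scheduled collection is Hour 27.
- Time after first dose: 75 − 1 = 74 h against 27 − 1 = 26 h; 26 / 74 = 35%.
- For an arm of 20: 20 × 74 / 24 = 61.7 patient-days if all reach Hour 75; 20 × 26 / 24 = 21.7 if all stop at Hour 27.
- Hour 27 is not a floor, because CCU exit or a safety end point can end participation sooner.

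**3. What unequal windows do to raw counts.** The documents give no distribution of CCU stay, so this is an illustration. Assume the same constant event rate in both arms.
- One arm all observed to Hour 75 (mean 74 h), the other half to Hour 27 and half to Hour 75 (mean (26 + 74) / 2 = 50 h): ratio of expected counts 50 / 74 = 0.68 with no true difference.
- Equal windows give 1.00. The extreme of all Hour 27 against all Hour 75 gives 0.35.

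**4. Acidosis markers.**
- End point: ketoacidosis.
- Chemistry abstracted: glucose, creatinine, eGFR (and HbA1c).
- Chemistry not listed: bicarbonate, anion gap, ketones, pH.
- Potential Risks says patients on insulin will not be included, but the Exclusion Criteria remove only those above a low-dose sliding scale. With the exclusions for type 1 diabetes and previous ketoacidosis, this lowers the expected number of cases but does not make the end point void.

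**5. What 20 per arm can show, whatever the window.** The plan gives no rate, size or power for any safety end point, so there is no figure of its own to reproduce here.
- Exact upper 95% limit for 0/20: 1 − 0.025^(1/20) = 16.8% two-sided; 1 − 0.05^(1/20) = 13.9% one-sided.
- For 0/40: 8.8% and 7.2%.
- Chance of 0/20, (1 − p)^20, for assumed in-window risks p of 1%, 2%, 5% and 10%: 82%, 67%, 36% and 12%.
- Fisher's exact test, 20 against 20: 4 against 0 gives p = 0.106; 5 against 0 gives p = 0.047.

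Step 5 describes the sample size. It does not measure the effect of the variable window, which is in steps 2 and 3.

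**The case against.** The case on the other side has several parts.

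- **Purpose.** This is a pilot. In the end-of-participation paragraph the safety end points act as triggers for the individual patient, which does not require informative rates. No between-arm safety test or safety claim is planned. That is fair and keeps the point minor, but end points that are listed will be tabulated by arm.
- **Ketoacidosis is a clinical adverse event.** A reader might infer that the plan means to detect it from glucose, or that glucose is the only chemistry recorded. The documents say neither. Creatinine and eGFR are also collected, and the CCU team can diagnose acidosis from the routine panel. What stands is that the study data will hold nothing to support or check such a diagnosis.
- **Event timing.** A reader might infer that these events mostly arise after the window closes, so that zero counts are a foregone conclusion. The documents give neither timing nor rates. Scaling assumed annual risks of 1% to 50% at constant hazard to 74 hours gives a 99.8% to 89.0% chance of zero events in 20 patients. That rests wholly on assumptions, and risk in acutely ill, instrumented patients could be higher. The point does not rely on it.
- **Sample size.** The 16.8% limit comes from 20 patients per arm and would be the same under any window. This stands in full.
- **Discharge also varies.** Following patients to discharge alone would replace one variable window with another, and patients may start or stop SGLT2i once participation ends. This stands, and is why the fix asks for a fixed period, patient-days and a record of later SGLT2i use.

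**Conclusion.** The point holds in a limited form. Observation for the item 3 events ends by about Hour 75, and sooner according to the patient's course. Scheduled time after the first dose can therefore differ nearly threefold between patients (26 against 74 hours), and raw counts by arm are not comparable. No acidosis marker is listed to support the ketoacidosis end point.

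The rules that close the window are stated in the plan. That the arms will in fact differ in time observed is a possibility, not a finding: the documents give no CCU stay by arm, and the 0.68 ratio is an illustration under a constant rate. A reader might go further and conclude that longer ascertainment would make the safety data informative. It would not: 0/20 still leaves 16.8%, so zero events would not be evidence of safety with or without the change.

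This is a low-cost improvement, not a flaw in the primary analysis.

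**What to change.** Add to the Safety End Points section:

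- For every randomised patient, whatever the reason for ending participation, ascertain the four events from the routine hospital record over one pre-stated fixed period from Hour 0. Use the same period in both arms, censored at discharge.
- Record any SGLT2i use after participation ends.
- Abstract bicarbonate and anion gap from the metabolic panel that already supplies glucose.
- Report counts by randomised arm with patient-days observed and exact confidence limits.
- State that 0/20 leaves a two-sided 95% upper limit of 16.8%, that this is due to sample size, and that zero events is not evidence of safety.

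The cost is a brief chart review of 40 patients at one centre, two extra data fields, and consent and data-use wording for information gathered after CCU exit. It needs no new tests, visits or staff and does not change clinical management. Two limits remain: discharge can still censor the arms differently, which patient-days will show but not remove, and later SGLT2i use may mix exposures, which the added record will make visible.
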